**Contact details for reporting SAEs**

**Fax: xxx, attention xxx**

**Please send SAE forms to: xxx**

**Tel: xxx (Mon to Fri 09.00 – 17.00)**

## **6. ASSESSMENT AND FOLLOW-UP**

The study will aim to recruit 40 patients and randomise them via computer generated random number allocation to either the VR intervention group or those having treatment as per routine protocol.

Both groups of patients will fill a pre and post procedural questionnaire. Pain and anxiety scores prior to the procedure and after the procedure will be compared against a control group of 20 patients for pain management by standard protocol. Scores will be measured by a Numeric Rating Scale (NRS) which is a validated measure of pain which is easy to use, has high compliance rates and is detects

meaningful changes in pain. The NRS is an 11-point scale consisting of integers from 0 through 10; 0 representing “No pain” and 10 representing “worst imaginable pain.” Respondents select the single number that best represents their pain intensity. Ratings of pre-operative anxiety were measured by an 11-point numeric rating scale. (NRS; Kindler et al., 2000): ‘How would you rate any anxiety you may currently be feeling’ 0 (no anxiety) and 10 (worst anxiety imaginable).

The VR intervention will involve watching a standard content of the video on a mobile device using a VR headset to distract them during the procedure. The duration of the video will be 15 minutes; but the video will only be played for the duration of the outpatient hysteroscopy. Patients are allowed to stop viewing the video if they so desire and this will be recorded.

A semi-structured interview will be conducted with the patients who have received the VR intervention, each lasting approximately 20 minutes. The semi structured interviews will allow for all participants to be asked similar question within a flexible framework.(Dearnley, 2005, Tindall, 2009) The interviews will be conducted within 30 minutes of the procedure, in a suitable location and will be recorded on a digital voice recorder. The questions will be focused on the women’s experiences of the procedure, in specific pain perception and questions around the VR intervention as well as any other aspect of their hospital care they felt to be relevant. If further clarification or exploration of any particular aspect of their care was required, the interview will readdress these topics before the end of the interview. Interviews will continue until no new information was being obtained, indicating that the theoretical saturation point had been reached. (Pope et al., 2000)

Clinician and nursing staff’s perception regarding feasibility of using the VR equipment was also assessed through a questionnaire. The clinician questionnaire will also assess the ease of the procedure and perceived pain scores for the patient.

Patient follow up will not be routinely arranged for the purpose of the study. Routine follow up as per clinical requirements will be arranged as routine for the procedure performed.

The study will end once the proposed numbers of patients have been recruited and data analysis completed. Participants will be debriefed after their participation in the study and will be directed to suitable support agencies if necessary.

## **7. STATISTICS AND DATA ANALYSIS**

The recruitment of women and interviewing proceeded alongside data coding and preliminary analysis.

Interviews will be transcribed verbatim and initially coded by reading and re reading the transcript and making notes, drawing on the observations made during the interviews and transcription. Transcripts will be coded line-by-line, describing, summarising and attending to linguistic elements such as pronoun and metaphor use. (Tindall, 2009) The transcripts will be entered into a qualitative software package (N6) and a thematic analysis undertaken from the emergent themes developed from these codes and cluster with related themes. Initial coding is Initial phase will involve open coding. Axial coding and selective coding with use of constant comparison will enable a cyclical and iterative process on the principles of grounded theory. Analytic frame for the analysis will be linked to the primary and secondary aims.

The statistically analysis will include statistical comparison of pre and post anxiety and pain scores as a function of membership of VR or control groups. Analysis of covariance (ANCOVA) will be used to determine whether the VR intervention led to a significantly difference between baseline and follow up pain and anxiety scores between VR and control arm.

Staff questionnaires will be analysed to correlate pain scores of actual vs. perceived and feasibility of carrying out the intervention will be assessed.

Demographic data would include age, parity, menopausal status and ethnicity.

Data and all appropriate documentation will be stored for a minimum of 10 years after the completion of the study, including the follow-up period.

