## **3. STUDY DESIGN**

The study is a randomised control trial involving mixed methods of qualitative and quantitative analysis. Participants will be recruited for the study at the Gynaecology Department at Whipps Cross University Hospital, Barts Health NHS Trust from June

2018 to October 2018. The patients will be identified from the gynaecology clinic by the clinicians who schedule them for Outpatient Hysteroscopy procedure. The study will include 40 patients attending the outpatient hysteroscopy clinic and randomised to either a VR intervention group or standard procedure by computer-generated randomisation.

They will be given a study information sheet, an invitation to participate with a reply slip to indicate whether they would like to participate in the study. Patients will be given standard pre procedural information about the procedure as per standard practice. Written informed consent will be obtained from participants and the interview outputs will be anonymised.

All patients will fill in a questionnaire before and after the procedure. Patients who have been randomised to the VR arm will have a semi-structured interview regarding their experience with VR.

The staff in the clinic will include a clinician performing the procedure and a staff nurse supporting the clinic. They will be given a study information sheet regarding the study and a written informed consent for a questionnaire will be obtained from them if they agree to participate. The clinician performing the procedure will fill in a questionnaire per patient regarding the ease of the procedure and perceived pain levels of the patient. The Clinician performing the procedure and nursing staff's perception regarding feasibility of using the VR equipment for each patient who had the intervention was also assessed through the questionnaire. The staff questionnaire responses will be anonymised by assigning a unique staff number for each of the staff. The list of the names of the staff and the study number allocated will be saved by the PI on a separate file.

Patient follow up will not be routinely arranged for the purpose of the study. Routine follow up as per clinical requirements will be arranged as routine for the procedure performed.

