## **8.2 CONSENT**

Consent to enter the study will be sought from each participant only after a full explanation has been given, an information leaflet offered and time allowed for consideration. Signed participant consent will be obtained. The right of the participant to refuse to participate without giving reasons will be respected. After the participant has entered the study the clinician remains free to give alternative treatment to that specified in the protocol at any stage if he/she feels it is in the participant's best interest, but the reasons for doing so will be recorded. In these cases the participants remain within the study for the purposes of follow-up and data analysis. All participants are free to withdraw at any time from the protocol treatment without giving reasons and without prejudicing further treatment.

In the event of the patient and the staff nurse consenting for the study but the gynaecologist not consenting for the procedure, the patient will be recruited and randomised as per protocol. In the event of the patient and the gynaecologist consenting for the study, but the staff nurse not consenting for the procedure, the patient will be recruited and randomised as per protocol. In these instances, the staff nurse and / or the gynaecologist will not fill the questionnaire and a note will be made.

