## APPENDICES

1. Patient Questionnaire
2. Semi structured interview questions for patients who have had the distraction technique (VR)
3. Staff Questionnaire
4. Patient information Leaflet

5. Staff Information Leaflet
6. Patient Consent form with reply slip.
7. Staff Consent form

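### Correlation is the only analysis named for clinician-perceived against patient-reported pain; it shows whether the ratings track each other, not whether clinicians rate too low or too high (minor)

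*Combined protocol and SAP*

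**What the plan says.** Section 3 (Study Design) provides the clinician's rating: "The clinician performing the procedure will fill in a questionnaire per patient regarding the ease of the procedure and perceived pain levels of the patient". Section 6 (Assessment and Follow-up) repeats this and calls the ratings scores: "The clinician questionnaire will also assess the ease of the procedure and perceived pain scores for the patient".

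The patient's pain is measured before and after the procedure on a 0-10 integer scale, described in Section 6: "Respondents select the single number that best represents their pain intensity". The scale and period of the clinician's item are not stated in the body of the protocol. The form is listed in the Appendices ("Staff Questionnaire") but is not reproduced in the text available.

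The only analysis named for the two ratings together is in Section 7: "Staff questionnaires will be analysed to correlate pain scores of actual vs. perceived". No coefficient is specified. The other quantitative analysis in that section is a "statistical comparison of pre and post anxiety and pain scores as a function of membership of VR or control groups", by ANCOVA. It concerns the two arms and does not pair clinician with patient scores.

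Section 8.2 allows for missing clinician forms. If the clinician does not consent, "the gynaecologist will not fill the questionnaire and a note will be made".

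**The concern.** Setting actual against perceived pain invites two questions. Do clinicians recognise which patients have more pain? Do they rate it at the right level? A correlation, Pearson or rank, addresses only the first. Adding a constant to every clinician rating leaves it unchanged, or nearly so on a scale cut off at 0 and 10.

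An analyst who follows Section 7 literally would report a coefficient and nothing else. A value around 0.7 could come from clinicians who are right on average or from clinicians who are well below their patients on average, and the reader could not tell which. The risk is that the coefficient is then read as agreement. Clinicians are to complete a form for each patient, so the resulting analysis ought to be interpretable.

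**Working it through.** The documents give no expected correlation, SD or power figure for this comparison, so there is nothing of the plan's own to reproduce.

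**Inputs**
- From the documents: at most 40 pairs (Sections 3 and 6) and a 0-10 integer patient scale (Section 6).
- Assumed: the clinician uses the same scale; patient scores have mean 5 and SD 2.5; rater noise has SD 2.2; the SD of the paired differences is 1.5 to 3.

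**Step 1: the identity.** For any constant a and any b > 0, corr(X, a + bY) = corr(X, Y). Take 40 constructed pairs with patient scores 2 to 9, each used five times (mean 5.5):

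| Clinician score | r | Mean difference (clinician minus patient) |
|---|---|---|
| Equal to patient | 1.00 | 0 |
| Always 2 lower | 1.00 | -2.0 |
| Always half | 1.00 | 2.75 - 5.5 = -2.75 |

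**Step 2: with noise and a bounded scale.** 400,000 simulated pairs per row, rounded and cut to 0-10. The SD of the paired differences comes out at about 2.

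| Downward shift | Pearson r | Spearman | Mean difference |
|---|---|---|---|
| 0 | 0.73 | 0.73 | 0.0 |
| 1 | 0.73 | 0.72 | about -0.9 |
| 2 | 0.72 | 0.72 | about -1.7 |
| 3 | 0.70 | 0.71 | about -2.45 |

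The cut at 0 and 10 makes the mean difference a little smaller than the shift.

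In simulated studies of 40 independent pairs, the middle 95% of r values is about 0.56 to 0.85 with no shift and 0.54 to 0.84 with a 2-point shift. The ranges nearly coincide. The corresponding ranges for the mean difference are -0.6 to 0.6 and -2.3 to -1.1, which do not overlap.

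**Step 3: precision of the alternative, pairs independent.** The 95% CI half-width for the mean paired difference is t(0.975, n-1) × SD / √n. For n = 40 and SD 2 this is 2.023 × 2 / √40 = 0.64.

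| SD of differences | 40 pairs | 30 pairs (10 assumed lost) |
|---|---|---|
| 1.5 | 0.48 | 0.56 |
| 2 | 0.64 | 0.75 |
| 2.5 | 0.80 | 0.93 |
| 3 | 0.96 | 1.12 |

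The limits of agreement lie 1.96 × SD either side of the mean difference, so ±3.9 points at SD 2. Each limit has a CI half-width of t × SD × √(1/n + 1.96²/(2(n-1))). At SD 2 this is 1.1 points with 40 pairs and 1.3 with 30.

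**Step 4: repeated ratings by one clinician.** The operating clinician fills in one form per patient, so a clinician may contribute many pairs. The documents give neither the number of clinicians nor an intraclass correlation. As an assumption, take 4 clinicians with 10 patients each and an intraclass correlation ρ of 0.1 to 0.3. The variance inflation is 1 + (10 - 1)ρ, which is 1.9 to 3.7, and its square root is 1.38 to 1.92. At SD 2 the half-width of 0.64 becomes about 0.9 to 1.2. Using degrees of freedom suited to so few clinicians would widen it further.

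**The case against.** The strongest reply is that the plan never asks whether clinicians over- or under-rate pain. Neither the objectives in Section 2 nor the outcome measures in Section 3.1 mention it. If the question is only whether clinician ratings follow patient ratings, a correlation is a reasonable answer. This stands. A reader might infer that the trial sets out to measure clinician bias and then picks a method that cannot detect it, but the documents do not support that. They leave the purpose unstated, and the gap is with a natural question rather than a written aim.

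It can also be said that the point rests on one verb in a loosely worded section, and that the authors may have meant compare. That is possible, but nothing in the text points to another method, and one sentence would settle it.

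Thirdly, the clinician's scale and rating period are not visible. If they differ from the patient's, a paired difference is not available and a rank correlation is the sensible choice. This also stands, and the fix below is conditional for that reason.

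Finally, where the scales match, the difference can be calculated later from the same data. A reader might infer that information will be lost. It will not be, unless the form uses a mismatched item, which is hard to repair afterwards.

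**Conclusion.** The point holds as a minor one. Section 7 names only correlation for the two ratings and does not state the purpose. Correlation carries essentially no information on the direction or size of a systematic offset: in the illustration a 2-point shift changes r by 0.01 and the mean difference by about 1.7 points. The algebra does not depend on the assumed inputs; the size of the illustration does.

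It would go too far to conclude that the trial's findings are at risk. The primary feasibility objective and the between-arm comparison of patient-reported scores do not use the clinician's ratings. It would also go too far to treat the Step 3 half-widths as what the study will achieve. They assume 40 complete and independent pairs, and are a best case if few clinicians rate most patients or some clinicians do not consent.

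**What to change.** First check in the staff questionnaire that the clinician's pain item uses the same 0-10 scale, and refers to the same period, as the patient's post-procedure score. If it does, replace the clause in Section 7 with:

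> The mean paired difference (clinician minus post-procedure patient score) with 95% CI and 95% limits of agreement will be reported, with the number of pairs and the number of clinicians, allowing for repeated ratings by the same clinician (using the staff numbers already assigned). The correlation will be given as description.

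If the scale or period differs, either align that one item or keep a rank correlation and state that it does not measure agreement.

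The cost is one sentence of analysis wording and possibly one questionnaire item, with no extra patients, staff or visits. The drawback is imprecision: even with 40 independent pairs and SD 2, each limit of agreement is known only to about ±1.1 points, and clustering by clinician will widen this. If only one or two clinicians take part, variation between clinicians cannot usefully be estimated, and the report should say that the result describes those clinicians.

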## **2. STUDY OBJECTIVES**

Primary objective:

- Feasibility of using virtual reality as a distraction technique in management of acute pain in patients undergoing Outpatient Hysteroscopy.

Secondary objectives:

- Understanding the acceptability and effectiveness of VR interventions within the procedural groups and how these might vary as a function of different patient demographics.
- Understanding the factors that might influence the willingness of patients to participate in a future formal trial of the technology.
- Understanding how best to implement the technology and designing of the contents of the VR intervention.
- Understanding the effective mechanisms for the analgesic effect of VR and explore how this could be tailored to individual patients.

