### **3.1 STUDY OUTCOME MEASURES**

Efficacy of VR in acute pain management

Feasibility of VR implementation during office gynaecology procedures

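### The sole primary objective, feasibility of VR, has no measure or denominator in the protocol body, and under its narrower wording a woman who refuses the headset supplies no feasibility evidence

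*Combined protocol and SAP*

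**What the plan says.** - **Objective.** Section 2 and the Study Summary list a single primary objective: "Feasibility of using virtual reality as a distraction technique in management of acute pain in patients undergoing Outpatient Hysteroscopy". Effectiveness is secondary: "Understanding the acceptability and effectiveness of VR interventions within the procedural groups".
- **Outcome measures.** Section 3.1 names two without defining or ranking them: "Efficacy of VR in acute pain management" and "Feasibility of VR implementation during office gynaecology procedures".
- **Analysis.** Section 7 says: "Staff questionnaires will be analysed to correlate pain scores of actual vs. perceived and feasibility of carrying out the intervention will be assessed". It adds that the framework for analysing the interviews will relate to the primary and secondary aims. It gives no count, rate, denominator or criterion for feasibility.
- **Staff form.** Section 3 describes the clinician's and nurse's "perception regarding feasibility of using the VR equipment for each patient who had the intervention was also assessed through the questionnaire". Section 6 repeats that staff views on feasibility come from a questionnaire, but does not restrict the patients concerned. Section 8.2 allows the form to be missing where a staff member does not consent.
- **Interviews.** Section 3: "Patients who have been randomised to the VR arm will have a semi-structured interview regarding their experience with VR". Section 6 confines the interviews to women who actually received VR, and so does the guide's title in the Appendices list. Section 6 also ends interviewing at saturation.
- **Stops and refusals.** Section 6 lets a patient stop the video and says that this is recorded. No analysis of the stops is specified, and no section mentions recording a refusal before the video starts.

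**The concern.** A woman allocated to VR who will not put on the headset is among the clearest evidence against feasibility. If the evidence comes only from women who used VR, it is drawn from those for whom delivery already succeeded, and VR will look more feasible than it is. This applies to interview themes and staff ratings as much as to a percentage.

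Because the body fixes neither the measure nor the women who count, two analysts following it faithfully could report different answers to the primary question from the same 20 women. The choice between them could be made after results are known.

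**Working it through.** **Step 1. What can be checked.** The planned total is 40 (sections 3 and 6) and the control group is 20 (section 6), so the VR arm is 40 − 20 = 20. The plan states no feasibility figure or threshold and no basis for the 40, so there is nothing further to reproduce.

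**Step 2. Who is covered, place by place.**

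| Source | Section 3 | Section 6 | Appendices list |
|---|---|---|---|
| Staff feasibility rating | patients who had VR | no limit stated | content not shown |
| Patient interview | all randomised to VR | those who received VR, until saturation | title: those who had VR |
| Record of stopping the video | not mentioned | yes, no analysis given | content not shown |
| Record of refusal before the start | not mentioned | not mentioned | content not shown |

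Combine section 3 for the staff form with section 6 for the interview, and a woman who refuses is in neither source. Combine section 6 for the staff form with section 3 for the interview, and she can be in both. The documents do not say which applies.

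**Step 3. What the denominator does.** Let *r* be refusals before the start and *s* be stops by the patient, both assumed. Completions are x = 20 − r − s.

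- Over all allocated: x / 20.
- Over women who had VR: x / (20 − r).

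Intervals are Clopper-Pearson 95%: the lower limit is the 0.025 quantile of Beta(x, n − x + 1) and the upper limit is the 0.975 quantile of Beta(x + 1, n − x). When x = n the lower limit reduces to 0.025^(1/n); for example 0.025^(1/16) = 0.794.

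| r | s | Over all allocated | Over women who had VR |
|---|---|---|---|
| 0 | 0 | 20/20 = 100% (83 to 100) | 20/20 = 100% (83 to 100) |
| 2 | 0 | 18/20 = 90% (68 to 99) | 18/18 = 100% (81 to 100) |
| 4 | 0 | 16/20 = 80% (56 to 94) | 16/16 = 100% (79 to 100) |
| 6 | 0 | 14/20 = 70% (46 to 88) | 14/14 = 100% (77 to 100) |
| 2 | 2 | 16/20 = 80% (56 to 94) | 16/18 = 89% (65 to 99) |
| 4 | 2 | 14/20 = 70% (46 to 88) | 14/16 = 87.5% (62 to 98) |

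With no stops, the rate among women who had VR stays at 100% however many refuse. The gap between the two columns is 0 points for no refusals and 30 points for 6.

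**The case against.** The strongest reply is that this is a mixed-methods study in which a qualitative answer on feasibility is planned and legitimate, that the questionnaires and interview guide are not shown and may contain feasibility items, and that nobody is lost from the trial. Much of this stands.

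- **The appendices.** They may well hold scored items, which is why the point is limited to the body. Even so, the body would still disagree with itself about which women the items cover.
- **Qualitative evidence.** Interviews and themes are a proper part of the answer. The question of who counts applies to them equally.
- **Refused women are still in the study.** A reader might infer that refusals disappear altogether. The documents do not support that. Both arms complete the patient questionnaires, and the clinician fills in a form for each patient unless he or she has not consented. Section 8.2 keeps patients in the analysis when the clinician gives alternative treatment. The number allocated is therefore recoverable; what is missing is a rule for using it and an explicit record of refusal.
- **The staff form.** A reader might infer that it definitely excludes women who refuse. Only section 3 says so; section 6 is open.
- **Efficacy named first in section 3.1.** A reader might infer that efficacy has displaced feasibility as the primary question. The list is unranked, and effectiveness is a declared secondary objective, so the analysis of covariance (ANCOVA) in section 7 is legitimate.
- **Willingness.** A reader might take the missing count of women invited as a failure to address "Understanding the factors that might influence the willingness of patients to participate in a future formal trial of the technology". That objective concerns the factors behind willingness, which a consent rate does not measure.

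**Conclusion.** The point holds in limited form and should be fixed; confidence is moderate because the appendices are unseen. The protocol body gives its only primary objective no measure and no denominator. It conflicts on who is interviewed and differs on which patients the staff feasibility form covers. It specifies no analysis of recorded stops and no record of refusal. On the narrower wording, women allocated to VR who refuse it contribute no feasibility evidence.

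The size depends on refusals, for which the documents give no figure. With the assumed 4 refusals the denominator alone moves the result by 20 points; with none it moves nothing. These figures rest on 20 women in the VR arm and on invented counts, so they show what is at stake and do not predict a result. The documents do not show that feasibility will in fact be overstated, only that the plan as written allows it.

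**What to change.** 1. **Name one primary feasibility measure in sections 3.1 and 7 before data are seen.** One example is VR started and viewed without being stopped by the patient, over all women allocated to VR, with an exact 95% CI. Record refusal before the start alongside the stops already recorded. Tabulate refusals, stops, equipment failures, and procedures abandoned or not done separately. The study team should fix in advance how each is classified.
2. **Reconcile the sections.** Sections 3 and 6 and the guide's title should agree on who is interviewed, and sections 3 and 6 on which patients the staff form covers, so that women allocated to VR who did not use it are included. State how this fits the saturation rule in section 6. Interviews and themes remain as supporting evidence.
3. **Optional.** Keep a count of women invited and report it as a recruitment rate only, not as a measure of the willingness factors. Report the ANCOVA as an adjusted difference with a 95% CI.

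**Cost.** A short refusal log and a wording amendment, which may need ethics notification. No extra patients are needed. The reported feasibility figure may become less favourable.
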